There are also data suggesting fatigue and signs of NMJ dysfunction in SMA patients (Montes 2010; Wadman. 2012; Montes 2014; Pera 2017).

Page 18

Three-Hz repetitive nerve stimulation showed a decremental compound muscle action potential in around half of SMA Types 2 and 3 patients, indicating an impaired NMJ transmission (Wadman 2012; Pera 2017). Furthermore, fatigue tested through 6MWT and expressed as decreased gait speed between first and last minute, is common in SMA Type 3 patients (Montes 2010; Pera 2017). This 6MWT pattern has not been found in other neuromuscular disorders, hence cannot be attributed to muscle weakness alone.

Based on the results of a randomized, double-blind, placebo-controlled, phase 3 clinical trial in SMA Types 1, nusinersen, is an antisense, intrathecally administered product designed to bind to the SMN2 pre-mRNA and promote inclusion of exon 7 (Finkel, 2017). It has been recently approved for treatment of all SMA types by FDA and European Medicines Agency. Furthermore, gene-replacement therapy using intravenous administration of adeno-associated virus 9 carrying SMN complementary DNA showed promising results in a small cohort of SMA Type 1 patients (Mendell, 2017). However, it is reasonable to assume that a single therapeutic solution may not be sufficient, hence combined treatments acting on different disease aspects may be beneficial.

In summary, recent studies in SMA animal models and SMA patients have shown that the NMJ displays significant structural and functional defects that precede overt disease symptoms, suggesting that impaired NMJ function may contribute to SMA pathogenesis and symptoms. Defects in the NMJ appear to precede degeneration of motor neurons suggesting that abnormal formation and/or maintenance of this structure may be a key event in disease pathogenesis. These defects have been observed at both the pre- and postsynaptic components of the NMJ, which likely contribute to the failure to maintain the NMJ and muscle innervation in mouse models of SMA. Finally, NMJ dysfunction has been also demonstrated in SMA patients, mainly in Type 3 subgroup, contributing to the symptoms associated with the disease.

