9.3.4 Method of Assigning Patients to Treatment Groups

Patients will be randomized on the last day of the open-label run-in period (Day 0), in a 1:1 ratio, to 1 of 2 treatment sequences (amifampridine for Period 1 and placebo for Period 2 or placebo for Period 1 and amifampridine for Period 2. IP will be administered under double-blind conditions. Randomized patients who discontinue after initiation of treatment may be replaced.

The randomization code will be provided to the unblinded Catalyst designee. Details will be included in the Pharmacy Manual.

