14.6.2 Secondary Efficacy Endpoint Analyses

The quantitative secondary efficacy endpoints (6-minute walk test, Time-to-rise-from-floor, Time-to-rise-from chair, Time-to-climb-4-stairs, and Time-to-walk-10 meters) will be analyzed as the HFSME is analyzed. The four CFB scores will be analyzed with a linear mixed model. Treatment and Sequence will be entered as fixed effects. Subject within Sequence will be entered as a random effect with a block-diagonal covariance structure. Population marginal means will be estimated for each of the four Period and Sequence combinations.

Results from INQoL questionnaires and PEDSQL TM inventory of disease specific symptoms will be summarized with descriptive statistics (n, mean, standard deviation, minimum, median, and maximum) per time point (Days 0, 7, 14, 21, and 28) and CFB, using the Day 0

¹ Also known as "LSMEANS".

Page 56

response as the baseline level). The subscales of the QoL questionnaires will be similarly summarized.

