### 10.2 General Statistical Considerations

The following standards will be applied for the analyses unless otherwise specified.

Simple summary statistics (descriptive statistics) for continuous data will be n (number of non-missing observations), mean, median, standard deviation, minimum, and maximum.

The frequency count and percentage will be used to summarize categorical data. Summary statistics will be presented by treatment by period and overall.

Summary statistics for all safety and efficacy variables will be presented by sequence, except for tables related to incidence of AEs which will be presented by treatment group.

All tables of baseline and demographic data will be presented by sequence.

All data collected will be presented in the by-patient data listings, sorted by patient and by period and day, where appropriate.

P-values < 0.05 will be considered as statistically significant.

95% confidence interval will be calculated as appropriate.

Change From Baseline (CFB) will be summarized for efficacy and safety assessments, where Baseline is defined as Day 0.

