# 10.3 Multiple Comparisons/ Multiplicity

No alpha adjustment for multiple comparisons will be introduced, because only the comparison between amifampridine and placebo group on the primary efficacy endpoint will be considered as confirmatory.

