# 10.11 Efficacy Analyses

The primary assessment of efficacy will be performed using the CFB in HFMSE total score. Secondary assessments of efficacy will be performed using the following endpoints:

- 1. CFB in 6-minute walk test (meters);
- 2. CFB in rising from floor (seconds);
- 3. CFB in rising from a chair (seconds);
- 4. CFB in climbing 4 steps (seconds);
- 5. CFB in walking 10 meters (seconds);
- 6. CFB in the INQoL subscales scores:

Symptoms (section 1):

- a) Weakness
- b) Muscle "locking"
- c) Pain
- d) Fatigue
- e) Droopy eyelids
- f) Double vision
- g) Swallowing difficulties

Life domains (section 2):

- a) Activities
- b) Independence
- c) Social relationship
- d) Emotions
- e) Body image

Life domains (section 3):

- a) Perceived treatment effects
- b) Expected treatment effects

Quality of Life

7. CFB in the PEDSQL score (where applicable).

The individual domain scores in INQoL and PedsQL will be calculated using the scoring algorithms outlined in Appendix 2.

The efficacy assessments will be summarized by sequence and period.

The change-from-baseline scores [Change From Baseline (CFB)7 = HFMSE7 – HFMSE0, CFB14 = HFMSE14 – HFMSE0, CFB21 = HFMSE21 – HFMSE0, CFB28 = HFMSE28 – HFMSE0] will be analyzed using a mixed effects linear model. Treatment (amifampridine (A) or placebo (P)) and Sequence (A/P or P/A) and the Treatment by Sequence interaction will enter the model as fixed effects. Subject within Sequence will enter the model as a random effect with a block diagonal covariance structure. The 95% confidence interval (CI) based on this model will be presented for the difference in the Least Squares (LS) means. The analysis will be performed using SAS PROC MIXED to incorporate the random effects model.

A summary statistics on the CFB in the individual items score of the HFMSE will be also provided by sequence and period.

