The quantitative secondary efficacy endpoints (6-minute walk test, Time-to-rise-from-floor, Time-to-rise-from chair, Time-to-climb-4-stairs, and Time-to-walk-10 meters) will be analyzed as the HFMSE is analyzed. The four CFB scores will be analyzed with a linear mixed model. Treatment and Sequence will be entered as fixed effects. Subject within Sequence will be entered as a random effect with a block-diagonal covariance structure. The 95% confidence interval (CI) based on this model will be presented for the difference in the Least Squares (LS) means. The analyses will be performed using SAS PROC MIXED to incorporate the random effects model.

Results from INQoL questionnaires and PEDSQL inventory of disease specific symptoms will be summarized with descriptive statistics (n, mean, standard deviation, minimum, median, and maximum) per time point (Days 0, 7, 14, 21, and 28) and CFB, using the Day 0 response as the baseline level). The subscales of the INQoL questionnaires will be similarly summarized.

Analysis of the primary efficacy endpoint will be perfored both in the FAS and in PPAS analysis set. Analysis on FAS analysis set will be considered as primary while analysis in the PPAS will be used as supportive of the FAS results.

Analysis of secondary efficacy endpoints will be performed only in the FAS analysis set.

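### The primary HFMSE model names no patient-by-period error term, so the sole confirmatory test can exceed its 5% level; separately, the secondary models' term list omits period

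*SAP*

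**What the plan says.** SAP 10.11 and Protocol 14.6.1 give the same primary model. The response is the change in HFMSE from Day 0 at each of Days 7, 14, 21 and 28. The fixed effects are treatment, sequence and their interaction. For the random part, "Subject within Sequence will enter the model as a random effect with a block diagonal covariance structure". The SAP names PROC MIXED but gives no RANDOM or REPEATED statement and no degrees-of-freedom option. From this model, "The 95% confidence interval (CI) based on this model will be presented for the difference in the Least Squares (LS) means".

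SAP 10.2 sets the threshold: "P-values < 0.05 will be considered as statistically significant". SAP 10.3 makes no alpha adjustment because "only the comparison between amifampridine and placebo group on the primary efficacy endpoint will be considered as confirmatory". SAP 6.1 expects about 12 patients, six per sequence, with no power calculation.

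For the five quantitative secondary endpoints, SAP 10.11 and Protocol 14.6.2 say that the analysis follows that of the HFMSE, but then state: "Treatment and Sequence will be entered as fixed effects". The interaction is not listed. Protocol 14.6.2 adds: "Population marginal means will be estimated for each of the four Period and Sequence combinations". The SAP drops that sentence. Protocol 14.8 gives the SAP precedence, while SAP 12 declares no departure from the protocol's analyses.

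**The concern.** **Primary model.** Treatment is assigned to a patient for a whole period, and the two visits in that period are repeat measurements of one treatment unit. The right yardstick for the treatment contrast is how much patients vary from period to period. Block diagonal says only that different patients are independent; it does not say how the four values within a patient are related. With a patient intercept as the only random term, anything shared by the two visits of a period is treated as independent noise. The standard error is then too small and the degrees of freedom too many.

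In a two-period crossover, patient-by-period variance also contains patient-to-patient variation in drug effect. The protocol's rationale gives some reason to expect such variation: Protocol 7.1 reports a "decremental compound muscle action potential in around half of SMA Types 2 and 3 patients". The requirement of a 3-point HFMSE gain in the run-in may reduce it, but nothing in the documents shows that it removes it.

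At stake are the only confirmatory p-value and its confidence interval.

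**Secondary models.** In this design the treatment-by-sequence interaction is the term that carries period. Without it, a period effect goes into the error if the sequences are equal in size and biases the treatment estimate if they are not. Unequal sequences are possible: "Randomized patients who discontinue after initiation of treatment may be replaced" (Protocol 9.3.4), and the documents do not say which sequence a replacement enters.

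**Working it through.** **Inputs.** 12 patients, 6 per sequence (SAP 6.1). Two visits in each of two periods (SAP 10.11), so 12 × 4 = 48 rows. Level 5% (SAP 10.2), taken as two-sided because the interval is 95%. Complete data assumed. Neither document gives a variance, so the visit residual variance is set to 1 and the patient-by-period variance to *r*, an assumption shown over a range.

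**Coding examined.** Fixed treatment, sequence and interaction; a random intercept per patient; independent residuals. The interaction spans the same space as period, so the primary model does adjust for period.

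**Degrees of freedom.** Fixed-effect and patient columns together have rank 14, so 48 − 14 = 34. These pool two sources:
- patient-by-period: 12 − 2 = 10 df, expected mean square 1 + 2*r*;
- visits within patient-period: 12 × 2 × 1 = 24 df, expected mean square 1.

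The critical *t* is 2.032 on 34 df and 2.228 on 10 df.

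**Variance of the treatment estimate.**
- True: (1 + 2*r*)/12.
- As estimated by the model, on average: [10(1 + 2*r*) + 24]/(34 × 12) = (1 + (20/34)*r*)/12.

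The two agree only at *r* = 0. There the statistic is exactly *t* on 34 df and the nominal 5% is reproduced. At *r* = 1 the true SE is √(3/12) = 0.500 and the model's is √(1.588/12) = 0.364, or 73%.

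**Type I error** (200,000 simulated trials per setting; separate reruns agreed to about 0.1 percentage point):

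| *r* | 0 | 0.1 | 0.25 | 0.5 | 1 | 2 |
|---|---|---|---|---|---|---|
| Model SE as % of true SE | 100 | 94 | 87 | 80 | 73 | 66 |
| Type I error, coding above (%) | 5.0 | 6.5 | 8.5 | 11.3 | 15.2 | 19.4 |
| Type I error, period means on 10 df (%) | 5.0 | 5.0 | 5.0 | 5.0 | 5.0 | 5.0 |

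REML fits of the planned model (200 data sets each) gave a mean SE of 0.289 at *r* = 0 (true 0.289) and 0.361 at *r* = 1 (true 0.500).

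**What could make *r* positive.**
- Individual drug effects with SD *s* are equivalent to *r* = *s*²/2. For *s* = 0.5, 1 and 1.41 visit-residual SDs, *r* = 0.125, 0.5 and 1, giving 6.9, 11.2 and 15.1%.
- Serial correlation alone, AR(1) with 0.3, 0.5 and 0.7, gives 8.4, 10.5 and 12.6%.

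**Would a different df be enough?** No. Keeping the model's SE but using 10 df gives 3.2, 6.0, 11.7 and 15.7% at *r* = 0, 0.25, 1 and 2. The missing error term is the main fault.

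**The other reading: an unstructured 4 × 4 block per patient.** Twelve patients must estimate 10 covariance parameters. In 8,000 REML fits at each of *r* = 0, 0.5, 1 and 2, without small-sample adjustment, the SE was 79% of the true value. Rejection was 11.1 to 11.7% on 10 df and 14.0 to 14.5% on 34 df.

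**Secondary term list.** Treatment plus sequence has rank 3, so it cannot freely estimate four period-by-sequence means. Let *p* be the period effect.
- Unequal sequences: the bias is (n_PA − n_AP)/N × *p*, in size 1/11 of *p* at 6/5 and 2/12 = 1/6 of *p* at 7/5.
- Equal sequences: no bias, but the expected mean square is (35 + 22*r* + 12*p*²)/35 on 35 df. With *p* = 1 visit-residual SD and *r* = 0, 0.5, 1, the model SE is 116, 91 and 81% of the true SE, and the type I error is 2.5, 7.3 and 11.3%.

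**The case against.** **The size is unknown.** No variance is given, so the inflation could be nil, and 15% or more needs patient-by-period variance at least equal to visit variance. This stands as a limit on size. It does not change the direction: any positive value inflates the test.

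**If the drug is inert, drug-effect variation is zero.** This is fair. The figures converted from drug-effect SDs apply, as type I error, only to a null in which individual benefits and harms average to zero. Under a wholly inert drug, only non-drug period fluctuation and serial correlation remain; an AR(1) of 0.3 already gives 8.4%. If the drug works unevenly, the same figures are the rate at which the 95% interval misses the mean effect.

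**The electrophysiology statement is weak support.** It covers unselected Types 2 and 3 and is not HFMSE response, whereas randomised patients have all passed the 3-point gate. This stands too. The statement shows only that uniform response cannot be taken for granted.

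**The inflation belongs to an inferred coding.** A programmer could add a per-patient treatment or period effect and obtain a different test. But the text names only Subject within Sequence, and wording that allows several tests, some of them invalid, has not pre-specified one.

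**The secondary issue nearly resolves itself.** The statement that these endpoints follow the HFMSE analysis restores the interaction, and SAP 12 declares no change from the protocol. That is right as to the likely intent. The two statements still conflict, on non-confirmatory endpoints.

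**This is a small Phase 2a trial.** True, but SAP 10.3 itself calls the comparison confirmatory.

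**Conclusion.** The concern holds. As written, the primary model does not identify the error against which treatment is tested. In the coding its words most naturally suggest, the sole confirmatory test holds 5% only at zero patient-by-period variance; it reaches 6.5% at a ratio of 0.1 and 15.2% at a ratio of 1. The alternative unstructured reading also exceeds 5% unless a small-sample adjustment is added. The degrees of freedom and the direction follow from the design; the size rests on assumed variance ratios, complete data and 6 patients per sequence. Because this affects the only confirmatory p-value and interval, it should be settled before unblinding. The secondary term list is a lesser wording conflict and has no bearing on the primary interval.

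**What to change.** **Primary model.** Before unblinding, specify one of:
1. fixed treatment, period and sequence (the same mean model as now); random Subject(Sequence) and Subject(Sequence) × Period; REML; Kenward-Roger degrees of freedom; or
2. the average of each patient's visits within a period, analysed as a standard crossover on 10 df.

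The two coincide with complete data and a positive estimate of the patient-by-period variance. The SAP should also say what is done if that estimate is zero. Under option 1 this happens in about 53, 13 and 4% of trials at *r* = 0, 0.5 and 1. The approximate type I error is then 3.4, 4.8 and 5.0% overall, conservative rather than inflated.

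**Secondary models.** Use the same model, including period, for the five quantitative endpoints and delete the reduced term list.

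**Cost.** A few lines of SAP text and one line of PROC MIXED code; SAP 4 already provides for review and revision before the unblinded analysis. The price is a wider primary interval. In visit-residual SDs, mean width goes from 1.16 to 1.25 at *r* = 0 (8% wider, the real cost), from 1.32 to 1.77 at *r* = 0.5 (34%) and from 1.46 to 2.17 at *r* = 1 (48%, from unrounded widths). In the last two cases the planned interval is too short.

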## 5.2 Study Design

This is a stratified, randomized (1:1), double-blind, placebo-controlled, 2-treatment, 2-sequence, crossover study.

Patients will be randomized (1:1) to one of two sequences:

AP: Amifampridine (Period 1) followed by Placebo (Period 2)

PA: Placebo (Period 1) followed by Amifampridine (Period 2)

Patients will be randomized on the last day of the open-label run-in period (Day 0).

IP will be administered under double-blind conditions. Randomized patients who discontinue after initiation of treatment may be replaced. The planned duration of participation for each patient is approximately 2 months, based upon length of dose titration and excluding the screening period, which can last up to 14 days.

The study is planned to be conducted in two investigational sites; and will include about 12 male and female SMA Type 3 patients.

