# 6 Sample Size, Randomization and Blinding

#### 6.1 Sample Size

The sample size for this study was based on clinical considerations related to the epidemiology of the disease, and not on a formal statistical power calculation. It is anticipated approximately 12 patients will be randomized with 6 patients per treatment sequence.

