## 11.2 Handling of Missing Data

If a patient discontinues during a double-blind treatment period and assessments are made upon discontinuation, then these values will be used as the assessments for that period. Otherwise, missing data due to discontinuation will not be imputed. Missing safety data will not be imputed.

Handling of missing data in INQoL is provided in the Appendix 2.

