#### 12 Changes from the Protocol

No changes from the statistical analyses planned in the study protocol have been introduced in this SAP.

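### SAP 10.11 gives two inconsistent models for the five quantitative secondary endpoints; the shorter one drops the period contrast, which can change the CI and, with unequal sequences, the estimate

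*SAP*

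**What the plan says.** SAP 10.11 describes the primary HFMSE model first. Treatment, Sequence and their product are fixed effects: "the Treatment by Sequence interaction will enter the model as fixed effects". Subject within Sequence is random, and the four change-from-baseline scores (Days 7, 14, 21 and 28) are the responses.

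For the 6-minute walk test, rise from floor, rise from chair, stair climb and 10-meter walk, the same section makes two statements in one paragraph:

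- These endpoints "will be analyzed as the HFMSE is analyzed".
- "Treatment and Sequence will be entered as fixed effects", with no interaction and no Period term.

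The reported result is a 95% CI for the LS-mean difference from this model.

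Protocol 14.6.2 contains the same pair of statements and adds an output: "Population marginal means will be estimated for each of the four Period and Sequence combinations". SAP 12 states: "No changes from the statistical analyses planned in the study protocol have been introduced in this SAP". Protocol 14.8 lets the SAP prevail over the protocol, but that cannot settle a conflict that the SAP also contains.

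**The concern.** A programmer who follows the cross-reference and one who follows the explicit list will fit different models and may report different intervals for the same endpoint. The omitted term is the only one in either model that carries a period shift. The 6-minute walk and timed tests are repeated at four blinded visits over four weeks, so a shift between periods from practice, fatigue or expectation cannot be ruled out in advance.

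At stake are the precision of the only model-based secondary results (quality of life is descriptive) and, if the sequences end up unequal, the estimate itself. An unresolved choice could also be settled after the results are seen.

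**Working it through.** **Inputs.** From the documents: two sequences, AP and PA (SAP 5.2); "approximately 12 patients will be randomized with 6 patients per treatment sequence" (SAP 6.1); two scores per period, four per patient; significance at 0.05 with 95% CIs (SAP 10.2), taken here as two-sided. The documents give no effect size, SD, power or period effect for these endpoints, so there is no stated figure to reproduce. Assumed: within-patient SD of one visit = 1; period effect π (Period 2 minus Period 1) of 0 to 1.5 SD; visits independent given the patient.

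**Step 1: the missing term is the period contrast.** Code A = +1, P = -1; AP = +1, PA = -1. The product is:

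| Cell | Treatment | Sequence | Product |
|---|---|---|---|
| AP, Period 1 | +1 | +1 | +1 |
| AP, Period 2 | -1 | +1 | -1 |
| PA, Period 1 | -1 | -1 | +1 |
| PA, Period 2 | +1 | -1 | -1 |

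The product is +1 throughout Period 1 and -1 throughout Period 2. The two-term model has three mean parameters for four cells, so it cannot fit the four Period and Sequence means freely. At 6:6 it misses each by half the period effect.

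**Step 2: complete 6:6 data.** The 48 scores from 12 patients leave 48 - 12 = 36 within-patient df: 34 after treatment and period, 35 after treatment alone. The point estimates coincide. An unmodelled period effect adds 48 × (π/2)² = 12π² to the residual sum of squares, so

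SE ratio = √[(35 + 12π²)/35].

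The power column is simulated, for a treatment effect of 0.8325 SD, which the full model detects with 80% power.

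| π (SD) | SE ratio, two-term model | Power, two-term model |
|---|---|---|
| 0 | 1.000 | 80% |
| 0.25 | 1.011 | 80% |
| 0.5 | √(38/35) = 1.042 | 78% |
| 1 | √(47/35) = 1.159 | 70% |
| 1.5 | √(62/35) = 1.331 | 58% |

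**Step 3: unequal sequences.** Let d be a patient's Period 2 mean minus Period 1 mean. Its expectation is π - τ in AP and π + τ in PA, where τ is the treatment effect.

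- The full model gives τ̂ = (d̄_PA - d̄_AP)/2 and π̂ = (d̄_PA + d̄_AP)/2.
- The two-term model averages A minus P over all patients: (n_PA d̄_PA - n_AP d̄_AP)/N = τ̂ + π̂ (n_PA - n_AP)/N.

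The gap depends on the estimated period effect. In the full model π̂ and τ̂ have the same SE, so with no true period effect the SD of the gap is |n_PA - n_AP|/N of the SE of τ̂. With a true period effect, the bias is π(n_PA - n_AP)/N. The last three columns are simulated.

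| AP:PA | Bias ÷ π (size); also gap SD ÷ SE | Models disagree on p<0.05 when π = 0, effect 0.83 SD | Type I error, two-term, π = 0.5 | Same, π = 1 |
|---|---|---|---|---|
| 7:5 | 2/12 = 1/6 (17%) | 3.9% | 5.0% | 4.8% |
| 6:3 | 3/9 = 1/3 (33%) | 10.8% | 6.7% | 10.3% |

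**Step 4: how often imbalance arises.** Assume random dropout from 6:6 in which a dropout contributes nothing and is not replaced. A bias of at least 1/3 of π then arises in 1.8% of trials at 10% dropout and 7% at 20%. Averaged over all splits, the two-term type I error at π = 0.5 and 1 SD is 4.6% and 3.2% (10% dropout), or 4.8% and 4.1% (20%). It is not inflated on average.

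**The case against.** The best defence is that the paragraph resolves itself. Its opening sentence sets the rule, the later sentence does not say that the two named effects are the only ones, and the four means in Protocol 14.6.2 need the full model. SAP 10.11 also summarizes efficacy by sequence and period, so a large shift would be visible. This stands as evidence of intent, and it is why the point is a correction rather than a dispute about design. It does not remove the conflict, because an explicit list of fixed effects is what gets programmed. The table shells mentioned in SAP 4 are not in the text available here, so whether they identify the model is unknown.

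A second defence is that serious imbalance is unlikely: "Randomized patients who discontinue after initiation of treatment may be replaced", and when assessments are made at discontinuation, "then these values will be used as the assessments for that period". This also stands in part, and Step 4 may overstate the frequency. But replacement is optional, and neither document says which sequence a replacement receives. A patient who leaves in Period 1 still has no Period 2 score.

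A reader might infer that the choice matters only if a material period effect exists. That holds for complete 6:6 data, apart from one df. It fails once the sequences are unequal, because a chance period difference then moves the estimate.

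A reader might also infer that the secondary analyses would produce excess false positives. The figures do not support that in general: type I error is below 5% at 6:6 when a period effect exists, is not inflated on average over random dropout, and rises materially only in splits such as 6:3.

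**Conclusion.** The inconsistency is real and appears in both documents. Under the two-term reading and complete 6:6 data, the estimate is unaffected and the SE is too large only if there is a period effect: about 4% at 0.5 SD and 16% at 1 SD, and about 1% at 0.25 SD. Under unequal sequences, the choice changes the estimate, the CI and sometimes significance even with no true period effect. A true period effect then biases the two-term estimate by 1/6 of its size at 7:5 and 1/3 at 6:3.

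Severity is low. The period effects are assumptions, SAP 10.3 treats only the primary endpoint as confirmatory, and the context favors the full model.

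One further inference should be resisted: that including the term secures a 5% type I error. The calculations treat visits within a period as independent given the patient. With an assumed patient-by-period SD of 0.7, simulated type I error is about 11% even with the term.

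**What to change.** Before unblinding, revise the secondary-endpoint paragraph of SAP 10.11 to name Treatment, Sequence and Treatment by Sequence (equivalently Treatment, Period and Sequence) for all five quantitative endpoints, matching the HFMSE model. The four means requested in Protocol 14.6.2 can then be estimated. SAP 4 provides for review and revision before the unblinded analysis, and Protocol 14.8 means that no protocol amendment is needed.

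The cost is a few words and one df (35 to 34 at N = 12 with complete data). With no period effect, the SE is multiplied by N/[2√(n_AP n_PA)]: 1.000 at 6:6, 12/(2√35) = 1.014 at 7:5, and 9/(2√18) = 1.061 at 6:3.

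The change removes bias from a shift between periods and nothing more. It does not address carryover, trend within a period, or extra correlation between visits in the same period.
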